1.2.1 Primary estimand(s)

The estimand is the precise description of the treatment effect and reflects strategies to address events occurring during trial conduct which could impact the interpretation of the trial results (e.g. premature discontinuation of treatment).

The primary clinical question of interest is: What is the effect of JDQ443 monotherapy in inducing radiological response per RECIST 1.1 assessed by BIRC when administered as first-line treatment for participants with locally advanced or metastatic NSCLC whose tumors harbor a KRAS G12C mutation and a PD-L1 expression < 1% (cohort A), regardless of study treatment discontinuation and any unforeseen events resulting from a public health emergency?

The justification for the primary estimand is that it will capture the treatment effect irrespective of study treatment discontinuation but avoids the confounding effect of any new anti-cancer therapy that is not a part of the originally assigned treatment.

The primary estimand is described by the following attributes:

1. Population: Adult participants with locally advanced or metastatic NSCLC without previous systemic treatment for metastatic disease whose tumors harbor a KRAS G12C mutation and a PD-L1 expression < 1%, irrespective of STK11 mutation status (cohort A).
2. Primary variable: BOR defined as the best response recorded from the start of the treatment until disease progression per RECIST 1.1 by BIRC, with responses documented after the use of any new anti-neoplastic therapy considered as non-response.
3. Treatment of interest: JDQ443 administered PO 200 mg twice a day continuously.
4. Handling of remaining intercurrent events:
 - Treatment discontinuation for any reason: Tumor assessment data collected irrespective of treatment discontinuation will be included to derive BOR (treatment policy strategy).
 - Any public health emergency as declared by local or regional authorities, i.e., pandemic, epidemic or natural disaster: tumor assessment data collected irrespective of such unforeseen events will be considered for the BOR (treatment policy strategy).
 - New anti-cancer therapy: If any new anti-neoplastic therapy is initiated, responses documented after the use of new anti-neoplastic therapy will be considered as nonresponse (composite strategy).
5. Summary measure: ORR defined as the proportion of participants with a confirmed CR/PR as BOR, with its corresponding two-sided exact binomial 95% confidence interval and a summary of the reasons for 'NE' BOR.

1.2.2 Secondary estimand(s)

One secondary clinical question of interest is: What is the effect of JDQ443 monotherapy in inducing radiological response per RECIST 1.1 assessed by BIRC when administered as first-line treatment for participants with locally advanced or metastatic NSCLC whose tumors harbor a KRAS G12C mutation, a PD-L1 expression $\geq 1\%$ and an STK11 co-mutation (cohort B), regardless of study treatment discontinuation and any unforeseen events resulting from a public health emergency?

The justification for the secondary estimand is that it will capture the treatment effect irrespective of study treatment discontinuation but avoids the confounding effect of any new anti-cancer therapy that is not a part of the originally assigned treatment.

This secondary estimand is described by the following attributes:

1. Population: Adult participants with locally advanced or metastatic NSCLC without previous systemic treatment for metastatic disease whose tumors harbor a KRAS G12C mutation, a PD-L1 expression $\geq 1\%$, and an STK11 co-mutation (cohort B).
2. Primary variable: BOR defined as the best response recorded from the start of the treatment until disease progression per RECIST 1.1 by BIRC, with responses documented after the use of any new anti-neoplastic therapy considered as non-response.
3. Treatment of interest: JDQ443 administered PO 200 mg twice a day continuously.
4. Handling of remaining intercurrent events:
 - Treatment discontinuation for any reason: Tumor assessment data collected irrespective of treatment discontinuation will be included to derive BOR (treatment policy strategy).
 - Any public health emergency as declared by local or regional authorities, i.e., pandemic, epidemic or natural disaster: tumor assessment data collected irrespective of such unforeseen events will be considered for the BOR (treatment policy strategy).
 - New anti-cancer therapy: If any new anti-neoplastic therapy is initiated, responses documented after the use of new anti-neoplastic therapy will be considered as non-response (composite strategy).
5. Summary measure: ORR defined as the proportion of participants with a confirmed CR/PR as BOR, with its corresponding two-sided exact binomial 95% confidence interval.

A further secondary clinical question of interest is: In participants who respond to the JDQ443 monotherapy based on RECIST 1.1 assessed by BIRC, how long does the response to first-line treatment for participants in cohort A or in cohort B last, regardless of study treatment discontinuation and any unforeseen events resulting from a public health emergency?

The justification for this secondary estimand is that it will capture the duration of the treatment effect irrespective of study treatment discontinuation but avoids the confounding effect of any new anti-cancer therapy that is not a part of the originally assigned treatment.

This secondary estimand will be evaluated for both cohorts and is described by the following attributes:

1. Population:
 - Cohort A: Adult participants whose best overall response by BIRC is CR or PR with locally advanced or metastatic NSCLC without previous systemic treatment for metastatic disease whose tumors harbor a KRAS G12C mutation and a PD-L1 expression $< 1\%$, irrespective of STK11 mutation status.
 - Cohort B: Adult participants whose best overall response by BIRC is CR or PR with locally advanced or metastatic NSCLC without previous systemic treatment for metastatic disease whose tumors harbor a KRAS G12C mutation, a PD-L1 expression $\geq 1\%$, and an STK11 co-mutation.
2. Primary variable: DOR defined as time from the date of first documented response of CR or PR to the date of the first documented progression or death due to any cause, according to RECIST 1.1 assessed by BIRC.
3. Treatment of interest: JDQ443 administered PO 200 mg twice a day continuously.
4. Handling of remaining intercurrent events:

- Treatment discontinuation for any reason: Tumor assessment data collected irrespective of treatment discontinuation will be included to derive DOR (treatment policy strategy).
- Any public health emergency as declared by local or regional authorities, i.e., pandemic, epidemic or natural disaster: tumor assessment data collected irrespective of such unforeseen events will be considered for the DOR (treatment policy strategy)
- New anti-cancer therapy: If any new anti-neoplastic therapy is initiated, progression or death occurring after the use of new anti-neoplastic therapy will not be considered and the DOR censored.

5. Summary measure: Median duration of response estimated by the Kaplan-Meier method (for cohort A and B, resp.).

2 Statistical methods

The demographic data will be summarized separately for cohort A, cohort B, the STK11-mutant participants pooled from the two cohorts, and all participants.

The efficacy analyses will be performed separately for each of the two cohorts and the STK11-mutant participants pooled from the two cohorts.

The safety analyses will be presented for cohort A, cohort B, STK11 mutant participants, and all participants.

2.1 Data analysis general information

The primary and final analyses will be performed by Novartis. SAS version 9.4 or later will be used to perform all data analyses and to generate tables, figures and listings. The futility interim analyses will also be performed by the Novartis team. Details and specifications for the analyses will be provided in an interim analysis plan.

2.1.1 Data included in the analysis

Data from all participants who signed the main informed consent will be used in the analysis. Data collected after participants' withdrawal of informed consent for further participation in the study will not be reported (except for death date, if it is obtained from public records [registers], local law and participant informed consent permitting). The date on which a participant withdraws full consent is recorded in the eCRF.

A cut-off date will be established for the primary analysis after the participants in the respective cohort who are still receiving study treatment will have completed at least 4 tumor assessments or discontinued study treatment earlier. If this criterion is reached earlier in one of the cohorts, the cut-off date and the primary analysis may occur at different times.

All statistical analyses will be performed using all data collected in the database up to the data cut-off date (per cohort, if applicable). All data with an assessment date or event start date (e.g. vital sign assessment date or start date of an adverse event) prior to or on the cut-off date will be included in the analysis. Any data collected beyond the cut-off date will not be included in the analysis and will not be used for any derivations.

All events with start date before or on the cut-off date and end date after the cut-off date will be reported as ‘ongoing’. The same rule will be applied to events starting before or on the cut-off date and not having a documented end date. This approach applies, in particular, to adverse event and concomitant medication reports. For these cases, the end date will not be imputed and therefore will not appear in the listings.

2.1.2 General analysis conventions

Pooling of sites: Unless specified otherwise, data from all study sites will be pooled for the analysis. Due to the expected small number of participants enrolled at sites, no site effect will be assessed.

Qualitative data (e.g., gender, race, etc.) will be summarized by means of contingency tables; a missing category will be included as applicable. Percentages will be calculated using the number of participants in the relevant analysis set or subgroup as the denominator.

Quantitative data (e.g., age, body weight, etc.) will be summarized by appropriate descriptive statistics (e.g. mean, standard deviation, median, percentiles, minimum, and maximum).

2.1.3 General definitions

2.1.3.1 Cohort assignment

The cohort of the participant will be assigned based on the entry in the “Study Treatment Assignment” eCRF.

2.1.3.2 Investigational drug and study treatment

Investigational drug as well as investigational treatment will be used to refer to JDQ443. The term investigational treatment may also be referred to as study treatment which is used throughout this document.

2.1.3.3 Date of first administration of study treatment

The date of first administration of study treatment is defined as the first date when a non-zero dose of study treatment is administered and recorded on the “Study Treatment” eCRF. For the sake of simplicity, the date of first administration of study treatment is also referred to as the start date of study treatment.

2.1.3.4 Date of last administration of study treatment

The date of last administration of the study treatment is defined as the last date when a non-zero dose of study treatment is administered and recorded on the “Study treatment” eCRF. This date will also be referred as last date of study treatment.

2.1.3.5 Study day

The study day describes the day of the event or assessment date, relative to the reference start date (start date of study treatment).

The study day is defined as:

- The date of the event (visit date, onset date of an event, assessment date etc.) – reference start date + 1 if event is on or after the reference start date;
- The date of the event (visit date, onset date of an event, assessment date etc.) – reference start date if event precedes the reference start date.

The reference date for all assessments (safety, efficacy, PK, PRO, etc.) is the start of study treatment.

The study day will be displayed in the data listings. If an event starts before the reference start date, the study day displayed on the listing will be negative.

2.1.3.6 Time unit

A year length is defined as 365.25 days. A month length is 30.4375 days (365.25/12). If duration is reported in months, duration in days will be divided by 30.4375. If duration is reported in years, duration in days will be divided by 365.25.

2.1.3.7 Baseline

For safety and efficacy evaluations, the last available assessment on or before the date of start of study treatment is defined as “baseline” assessment.

If labs with duplicate laboratory measurements taken at the last assessment date on or before the start date of study treatment, then the rule described below will be applied for the calculation of baseline.

If values are from central and local laboratories, the value from central assessment should be considered as baseline.

For gradable labs:

- The value of lower CTCAE grade will be considered as the baseline value.
- If several records have the same absolute grade, but in different directions, two baselines should be created, the record with grade below 0 should be the baseline of the 'Hypo' parameter, and the other record should be the baseline for the 'Hyper' parameters.

For non-gradable labs:

- If both within normal range: take average value
- If one within normal range and the other outside: take the one within normal range
- If both outside normal range: take the one closest to the normal range

If participants have no value as defined above, the baseline result will be missing.

2.1.3.8 On-treatment assessment/event and observation periods

For adverse event reporting the overall observation period will be divided into three mutually exclusive segments:

1. ***pre-treatment period:*** from day of participants informed consent to the day before first administration of study treatment

2. **on-treatment period:** from date of first administration of study treatment to 30 days after date of last actual administration of study treatment (including start and stop date)
3. **post-treatment period:** starting at day 31 after last administration of study treatment.

Safety summaries (tables, figures) and summaries of on-treatment deaths include only data from the on-treatment period with the exception of baseline data which will also be summarized where appropriate (e.g. change from baseline summaries). In addition, all deaths which occurred during the study (i.e. during the on-treatment, and post-treatment periods) will be summarized.

An on-treatment adverse event (or treatment-emergent AE) is defined as any adverse event reported in the on-treatment period.

An on-treatment assessment is defined as any assessment performed during the on-treatment period.

In case at the time of the analysis, the date of last administration of study treatment is missing, on-treatment adverse events/assessments include any adverse event/assessment recorded in the database and which occur after the start date of the study treatment.

Data listings will include all assessments/events, flagging those which were collected during the pre-treatment and post-treatment period.

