7.1.1 Follow-up for safety evaluations

All treated participants should have a safety follow-up conducted at least 30 days after the last administration of study treatment. All SAEs reported during this time period must be reported as described in Section 8.7.3

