9.4.2 Safety endpoints

For all safety analyses, the safety set will be used. All listings and tables will be presented by cohort.

Safety summaries (tables, figures) include only data from the on-treatment period with the exception of baseline data which will also be summarized where appropriate (e.g., change from

baseline summaries). In addition, a separate summary for death including on treatment and post treatment deaths will be provided. In particular, summary tables for adverse events (AEs) will summarize only on-treatment events, with a start date during the on-treatment period (treatment-emergent AEs).

The overall observation period will be divided into three mutually exclusive segments:

- 1. Pre-treatment period: from day of participant's informed consent to the day before first dose of the study treatment
- 2. On-treatment period: from day of first dose of the study treatment to 30 days after last dose of the study treatment
- 3. Post-treatment period: starting at day 31 after last dose of the study treatment.

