2.1.3.9 Windows for multiple assessments

In order to summarize data collected over time (including unscheduled visits), the assessments will be time slotted. The following general rule will be applied in creating the assessment windows: If more than one assessment is available in the same time window, the assessment closest to the planned date will be used. If 2 assessments within a time window are equidistant from the target date, then the earlier of the 2 assessments will be used. If there are multiple assessments on the same date, then the worst case will be used.

The following tables define time windows for descriptive summary of PRO ([Table 2-1](#) to [Table 2-4](#)) and ECOG performance status (Table 2-1) data by visit and longitudinal data analysis planned in [Section 2.11](#).

Table 2-1 Time windows for ECOG PS

Assessment	Target study day of assessment	Time interval
Baseline	≤ 1	≤ Study days 1
Cycle 2 Day 1	22	Study days 2 to 32
Cycle 3 Day 1	43	Study days 33 to 53
Cycle k Day 1 (k≥ 4)	d=(k-1)×21+1	Study days d-10 to d+10
		For last cycle of dosing: from (k-1)×21-9 to EOT disposition date + 7 days
		Note: EOT visit data are included if obtained within 7 days of

Assessment	Target study day of assessment	Time interval
Safety follow-up	EOT + 30	permanent discontinuation of study treatment. From EOT disposition date + 8 days to 44 days after the EOT disposition date

Table 2-2 Time windows for PRO: NSCLC-SAQ, [REDACTED], [REDACTED], [REDACTED]

Time window	Planned visit timing	Time window definition
Baseline	$\leq 1^*$	\leq Study day 1^*
On treatment		
Cycle 1 Day 8	8	Study days 2 – 11
Cycle 1 Day 15	15	Study days 12 – 18
Cycle 2 Day 1	22	Study days 19 – 25
Cycle 2 Day 8	29	Study days 26 – 32
Cycle 2 Day 15	36	Study days 33 – 39
Cycle 3 Day 1	43	Study days 40 – 46
Cycle 3 Day 8	50	Study days 47 – 53
Cycle 3 Day 15	57	Study days 54 – 60
Day 1 of every cycle from Cycle 4		
Cycle 4 Day 1	64	Study days 61 – 74
Cycle 5 Day 1	85	Study days 75 – 95
Cycle k Day 1 ($k = 4, 5, \dots$)	$d = (k-1) \times 21 + 1$	Study days $(k-1) \times 21 - 9$ to $(k-1) \times 21 + 11$ For last cycle of dosing: from $(k-1) \times 21 - 9$ to EOT disposition date +7 Note: EOT visit data are included if obtained within 7 days of permanent discontinuation of study treatment.
Post treatment		
Efficacy follow-up, every 12 weeks		
Efficacy follow-up 1	12 weeks after EOT disposition date + 7 days	From EOT disposition date + 8 days to 18 weeks after EOT disposition date + 7 days

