2.9 Analyses supporting secondary objectives – safety

For all safety analyses, the safety set will be used. All listings and tables will be presented by cohort.

Safety summaries (tables, figures) include only data from the on-treatment period as defined in [Section 2.1.3.8](#), with the exception of baseline data which will also be summarized where appropriate (e.g., change from baseline summaries). In particular, summary tables for adverse events (AEs) will summarize only on-treatment events, with a start date during the on-treatment period (treatment-emergent AEs). In addition, a separate summary for deaths including on-treatment and post-treatment deaths will be provided.

All safety data, regardless of observation period, will be listed and assessments collected in the post-treatment period will be flagged in the listings.

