2.9.4.3 ECOG performance status

The performance status will be assessed according to the ECOG performance status scale as specified in [Table 2-7](#) below, ranging from 0 (most active) to 5 (least active).

Table 2-8 ECOG performance status

Grade	ECOG status
0	Fully active, able to carry on all pre-disease performance without restriction
1	Restricted in physically strenuous activity but ambulatory and able to carry out work of a light or sedentary nature e.g., light house work, office work
2	Ambulatory and capable of all self-care but unable to carry out any work activities. Up and about more than 50% of waking hours
3	Capable of only limited self-care, confined to bed or chair more than 50% of waking hours
4	Completely disabled. Cannot carry on any self-care. Totally confined to bed or chair
5	Dead

The rules and time windows defined in [Section 2.1.3.9](#) will be used to group the ECOG PS data over time.

Frequency counts and percentages of participants in each score category will be provided by time point for the on-treatment period. Shift tables of ECOG performance status at baseline to worst post-baseline ECOG performance status by score will be provided by cohort using the safety set. ECOG performance status at each time point will be listed.

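### SAP 2.9.4.3 defines an ECOG safety follow-up time point but counts only on-treatment data, so compliant follow-up visits on days 31 to 37 drop out of that row

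*SAP*

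**What the plan says.** **The cut-off.** Protocol 9.4.2 defines the period as "On-treatment period: from day of first dose of the study treatment to 30 days after last dose of the study treatment". SAP 2.1.3.8 adopts it, counting "from date of first administration of study treatment to 30 days after date of last actual administration of study treatment (including start and stop date", with day 31 opening the post-treatment period. It adds: "An on-treatment assessment is defined as any assessment performed during the on-treatment period". SAP 2.9 makes this a general rule: "Safety summaries (tables, figures) include only data from the on-treatment period as defined in" Section 2.1.3.8, baseline excepted. SAP 2.9.3 (laboratory) and 2.9.4.2 (vital signs, with weight among the parameters) repeat it.

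**ECOG.** SAP 2.9.4.3 says that the Section 2.1.3.9 windows "will be used to group the ECOG PS data over time", and that the frequency counts "will be provided by time point for the on-treatment period". In those windows, Table 2-1 has a Safety follow-up row with target EOT + 30 and this interval: "From EOT disposition date + 8 days to 44 days after the EOT disposition date".

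**The visit.** Protocol 7.1.1 states: "All treated participants should have a safety follow-up conducted at least 30 days after the last administration of study treatment". Protocol Table 1-2 gives the visit a window of +7 days with no minus side. Protocol Table 1-3 schedules hematology, chemistry, vital signs, weight and ECOG there.

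**What happens to later values.** SAP 2.9 lists all safety data from every period and flags those collected post-treatment.

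**The concern.** Two instructions in SAP 2.9.4.3 pull against each other. Table 2-1 provides a time point wide enough to catch the safety follow-up visit whenever the protocol permits it. The on-treatment restriction then removes seven of the eight permitted days. Which participants appear in the row depends largely on whether the site saw them on exactly day 30, and nothing in the plan would tell a reader of the table so.

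The same cut-off reaches the other assessments at this visit. After EOT it is the only scheduled laboratory, vital-sign, weight and ECOG assessment. An abnormality first seen there on days 31 to 37 would be listed but would not enter the worst-grade, shift or notable-value tables. Participants who stop for progression, for example, have no scheduled tests between EOT and this visit.

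**Working it through.** The plan gives no figure to reproduce. The check is a day count, with days numbered after the last dose.

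**Inputs**
- On-treatment period: through day 30 inclusive (SAP 2.1.3.8, protocol 9.4.2).
- Earliest safety follow-up: day 30 (protocol 7.1.1). Latest in-window: 30 + 7 = day 37 (protocol Table 1-2).
- ECOG Safety follow-up slot: EOT disposition date + 8 to + 44, target + 30 (SAP Table 2-1).
- Gap *e* from last dose to EOT disposition date: not given. I assume 0 to 7 days, from the 7-day EOT limit in protocol Table 1-2, and then test longer gaps.

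**Step 1: permitted days against the cut-off.** Permitted days are 30 to 37, so 37 − 30 + 1 = 8. Day 30 is on-treatment (1 of 8). Days 31 to 37 are post-treatment (7 of 8).

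**Step 2: the ECOG row.** The slot covers days *e* + 8 to *e* + 44. It holds all of days 30 to 37 when *e* + 8 ≤ 30 and *e* + 44 ≥ 37, that is, for *e* from 0 to 22.

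| *e* | Slot (days) | Permitted days in slot | Of these, on-treatment | Row target (*e* + 30) |
|---|---|---|---|---|
| 0 | 8–44 | 8 of 8 | 1 of 8 | day 30 |
| 7 | 15–51 | 8 of 8 | 1 of 8 | day 37 |

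The row's own target day is on-treatment only when *e* = 0.

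**Step 3: what else can enter the row.** The on-treatment part of the slot is 30 − (*e* + 8) + 1 = 23 − *e* days, so 23 days at *e* = 0 and 16 at *e* = 7, out of 37. SAP 2.1.3.9 slots unscheduled visits too, so an early or unscheduled ECOG in that stretch is counted. None is scheduled there.

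**Step 4: share of in-window visits lost.** The documents give no visit-timing data, so this is a range.

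| Assumed timing | Lost |
|---|---|
| Every visit on day 30 | 0% |
| Day 30 used whenever it is a weekday (Monday–Friday clinics, last doses even over the week) | 2/7 = 28.6% |
| Even over days 30 to 37 | 7/8 = 87.5% |

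In the last case, with full attendance, the visits tabulated would be 90 × 1/8 = 11.25 (about 11 of 90) in cohort A and 30 × 1/8 = 3.75 (about 4 of 30) in cohort B.

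**Step 5: longer EOT gaps.** Protocol 6.5.1 lets an interruption run to 21 days before discontinuation is required, while the on-treatment clock starts from the last dose actually taken. If *e* exceeds 22, the slot starts after day 30. At *e* = 23 it starts on day 31, holds 7 of the 8 permitted days, and none of them is on-treatment.

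**Step 6: after the change.** A limit of day 37 for the scheduled visit keeps 8 of 8 permitted days for *e* from 0 to 22. Beyond that, the visit must be assigned by name rather than by the slot.

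**The case against.** The strongest reply is that the 30-day limit is a prespecified convention. Protocol 9.4.2 sets it, the SAP follows it, and it matches the 30 days of AE collection. One window for AEs and laboratory values is defensible, and the visit's nominal day lies inside it. For laboratory, vital-sign and weight summaries this stands. A reader might infer that the SAP is in error there; the documents do not support that.

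A reader might also infer that only a day-30 result can ever be tabulated, or that the ECOG row will be almost empty. Neither follows. Early and unscheduled assessments from EOT + 8 to day 30 count, and the distribution of visit days is unknown. If every site used day 30, nothing would be lost.

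The consequences are also limited. Excluded values are listed and flagged, and EOT results are summarized. Protocol 6.5.3 requires at least weekly follow-up for 4 weeks when treatment is interrupted or stopped for an AE or a clinically significant laboratory value. That safeguard does not cover participants who stop for other reasons.

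None of this settles the ECOG mismatch. A convention for AE onset does not explain why a follow-up row reaching EOT + 44 is defined and then cut at last dose + 30.

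**Conclusion.** The ECOG point holds. SAP 2.9.4.3 uses a safety follow-up time point that accepts every permitted visit day and then keeps 1 of 8, so the row is filled selectively. The day count comes directly from the documents. The 8-of-8 acceptance assumes an EOT gap of 22 days or less, which includes the expected 0 to 7. The effect on the table cannot be sized beyond 0% to 87.5% of in-window visits, and both ends rest on assumed visit timing.

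For laboratory, vital-sign and weight results, the exclusion of days 31 to 37 is a consistent application of protocol 9.4.2. Including them would be an improvement, not a correction. The impact is modest throughout, and no efficacy result is touched.

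**What to change.** **Needed.** In SAP 2.9.4.3, state that the Safety follow-up row includes the scheduled safety follow-up visit through last dose + 37 days, and that all data through day 30 stay in as now. Assign the visit by name where a long interruption before EOT moves the slot. The cost is a sentence and a small programming change for one visit.

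**Worth doing at the same time.** In SAP 2.9.3 and 2.9.4.2, add the scheduled safety follow-up laboratory, vital-sign and weight results from days 31 to 37 to the summaries. For these, require that no new antineoplastic therapy has started, and apply that condition only to days 31 to 37, so that no value now summarized is removed. Add a footnote that late values may reflect disease and that this window is 7 days longer than the one for AEs. Record the departure from protocol 9.4.2, and let that note cover the ECOG row as well. The downside is that a day-35 laboratory value could be tabulated while an AE with the same onset is not treatment-emergent; the footnote should make that plain.

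Leave the AE on-treatment period at 30 days. Deleting the Table 2-1 row is not a good alternative, because on-treatment ECOG data between EOT + 8 and day 30 would then have no time point.
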